3 LIST OF ABBREVIATIONS AND DEFINITIONS OF TERMS

The following abbreviations and special terms are used in this study protocol.

Table 2: Abbreviations and Special Terms

| Abbreviation or specialist term | Explanation |
|---------------------------------|---|
| AUC | Area Under the Plasma Concentration versus Time Curve |
| BPI-DPN | Brief Pain Inventory for Diabetic Peripheral Neuropathy |
| CFR | Code of Federal Regulations |
| C _{max} | Plasma Concentration |
| CSF | Cerebrospinal fluid |
| DSIS | Daily Sleep Interference Scale |
| eCRF | Electronic case report form |
| FDA | Food and Drug Administration |
| GAD | Generalized Anxiety Disorder |
| GCP | Good Clinical Practice |
| HADS | Hospital Anxiety and Depression Scale |
| HbA1c | Hemoglobin A1c; glycated hemoglobin |
| HCV RNA | Hepatitis C Virus-Ribonucleic Acid |
| HIV | Human Immunodeficiency Virus |
| ICH | International Conference on Harmonisation |
| IRB | Institutional Review Board |
| MDD | Major Depressive Disorder |
| MDE | Major Depressive Episode |
| NF | National Formulary |
| NMDA | N-methyl-D-aspartate |
| NMDAR | N-methyl-D-aspartate receptor |
| NRS | Numerical Rating Scale |
| PGI-C | Patient Global Impression of Change |
| QOL-DN | Norfolk Quality of Life Questionnaire - Diabetic Neuropathy |
| SF-MPQ-2 | Short-Form McGill Pain Questionnaire version 2 |
| S-STS | Sheehan Suicidality Tracking Scale |
| TEAE | Treatment-emergent adverse events |
| USP | United States Pharmacopeia |

Note: Abbreviations that appear only in tables or figures are defined in the appropriate tables or figures.

4 INTRODUCTION

NYX-2925 is a novel small molecule being developed for the treatment of neuropathic pain and fibromyalgia. NYX-2925 is an *N*-methyl-D-aspartate receptor (NMDAR) functional glycine-site partial agonist, and at low concentrations of endogenous agonist (glycine or D-serine), NYX-2925 partially activates NMDAR. NYX-2925 appears to act at a binding site that is distinct from NMDAR agonists or antagonists studied to date, such as D-cycloserine, ketamine, MK-801, or kynurenic acid. The NYX-2925 mode of action is distinct from that of all of existing and emerging drugs that are indicated for the treatment of neuropathic pain and fibromyalgia. While current medications target individual elements of pain signal transmission or modulation, NYX-2925 modulates multiple synaptic relays within pain circuits.

Glutamate is the major excitatory neurotransmitter in the central nervous system and acts through activation of glutamate receptors. A portion of the receptors bind preferentially to *N*-methyl-D-aspartate (NMDA), and are therefore, termed NMDARs. Unlike other glutamate receptors found in the brain, such as α-amino-3-hydroxy-5-methyl-4-isoxazolepropionic acid or kainic acid receptors, the NMDARs are unique in that they have distinct binding sites for both glutamate and glycine, and binding by both ligands is required for receptor activation. The NMDARs are implicated in a number of physiological and pathological processes, including anxiety, cognition, learning, stroke, schizophrenia, Parkinson's disease, and neuropathic pain (Traynelis 2010, Mony 2009, Tai 2001).

The central nervous system modulates the experience of pain in people with neuropathic pain, with the rostroventralmedial medulla (Silva 2016), the dorsal anterior cingulate cortex (Russo 2015), the insula and other brain regions (Ossipov 2010) all thought to be involved. Neuropathic pain is caused by disease or injury of the somatosensory system as opposed to nociceptive pain where the sensory system is physiologically normal (Jensen 2014). While neuropathic pain can initially arise within the central or the peripheral nervous system through a wide range of etiologies, central nervous system modulation of the experience of pain is common, regardless of the specific precipitating factors or initial location of the pain. The prevalence of neuropathic pain is approximately 8% in the population in the United States (Gilron 2015, Toth 2013, Bouhassira 2008). Individuals suffering from neuropathic pain, irrespective of the underlying disorder, currently have limited treatment options available. Current treatment options predominantly include antidepressants and antiepileptics. These therapies have shown some efficacy in treating neuropathic pain symptoms, although for a large proportion of patients, treatment is insufficient.

Preclinical pharmacology studies support the study of NYX-2925 in both fibromyalgia and neuropathic pain, both of which are chronic pain syndromes involving central nervous system modulation of pain signals. NYX-2925 is effective in several models of neuropathic pain, and has been shown to be effective in the chronic unpredictable stress model of fibromyalgia. Animal models of neuropathic pain in which NYX-2925 was tested include the rat Bennett model of neuropathic pain, the rat streptozotocin model of diabetic peripheral neuropathy, and the rat Taxol® model of chemotherapy-induced neuropathic pain. Unlike gabapentin (150 mg/kg orally), NYX-2925 (1 to 30 mg/kg orally) produced a rapid and long-lasting analgesia in the rat Bennett model of neuropathic pain without changes in locomotor activity after a single dose. Further, in

the chronic unpredictable stress model of fibromyalgia, NYX-2925 (10 mg/kg) has been shown to produce mechanical analgesia. In summary, these data support testing NYX-2925 in both fibromyalgia and neuropathic pain.

Pharmacokinetic studies have been performed in rats and dogs, and suggest that NYX-2925 is rapidly absorbed into the bloodstream, and time to peak plasma concentration is reached within 1 hour. NYX-2925 is rapidly eliminated from plasma with an apparent terminal elimination half-life in the range of 1 to 2 hours. Brain exposure is approximately 5% to 10% relative to plasma levels of NYX-2925.

Both single-dose and daily repeat-dose toxicology studies have been performed in rats and dogs. The maximum tolerated dose following a single oral exposure is at least 1000 mg/kg in both rats and dogs. After 6 weeks of daily oral doses, the no-observed-adverse-effect levels were the highest doses tested (180 mg/kg in dogs and 480 mg/kg in rats). There were no adverse findings in either species. The plasma levels (exposure) of NYX-2925 at the highest doses in these studies are considered to be at least 50- to 100-fold the projected human therapeutic dose.

NYX-2925 has been administered to humans. The first-in-human study (NYX-2925-1001), for which results are available, was a combined single and multiple ascending dose, placebocontrolled study in healthy volunteers that also includes food-effect, cerebrospinal fluid (CSF), and elderly cohorts.

In the single dose portion of the study, single doses of NYX-2925 were administered orally. Five ascending dose groups (50 mg, 150 mg, 400 mg, 800 mg, and 1200 mg) and an elderly cohort (300 mg) with 8 subjects each (6 on active drug, 2 on placebo in each group) were dosed. Seven days after the initial dose, the 400 mg dose group received a second repeated dose (6 active drug, 1 placebo) to examine the effect of food on plasma drug concentrations. A CSF cohort (50 mg) was also completed with 6 subjects receiving NYX-2925. In 7 dose groups or cohorts, 29 males and 25 females were enrolled. A total of 52 of the 54 single dose subjects completed the study. Two subjects randomized to placebo discontinued study participation. One subject was lost to follow-up and 1 subject discontinued due to physician decision (related to subject noncompliance). One subject in the elderly cohort receiving 300 mg experienced a treatment-emergent adverse event (TEAE) which was not considered related to NYX-2925. Five subjects in the CSF cohort receiving 50 mg experienced at least one TEAE, one of which (procedural headache) was deemed related to NYX-2925. One subject receiving placebo experienced a TEAE. There were no TEAEs reported for clinical laboratories, safety electrocardiograms, or vital signs.

In the multiple ascending dose phase, there were three ascending dose groups (150, 600 and 900 mg) with 8 subjects in each dose group; 6 received active drug and 2 received placebo for up to 7 days. There were also 6 subjects in the CSF cohort who were dosed with NYX-2925 300 mg (no placebo control) and 5 completed the study. A total of 15 males and 15 females were enrolled. Study medication was given once daily for up to 7 days. Two subjects in the CSF cohort discontinued study participation, 1 due to other (related to subject noncompliance) and 1 due to protocol violation. All subjects in 150 mg, 600 mg, and 900 mg dose groups received all 7 doses of study medication. Twelve subjects (1 NYX-2925 150 mg, 3 NYX-2925 600 mg, 1 NYX-2925 900 mg, 2 placebo, and 5 NYX-2925 300 mg CSF cohort) reported at least 1 TEAE. There was one subject in the 150 mg dose group with urinary retention assessed as unrelated by the investigator, and possibly related by the sponsor. There was 1 subject with at least 1 study drug

related TEAE (flatulence and bloating) in the 600 mg dose group, 1 placebo subject with at least 1 study drug related TEAE (fatigue and lethargy), and 1 CSF cohort subject with at least 1 study drug related TEAE (headache). No grade 3 or higher TEAEs, serious TEAEs, or TEAEs leading to study discontinuation were reported. No individual preferred adverse event term was reported for more than 1 subject in the 150 mg, 600 mg, or 900 mg dose groups. In the CSF cohort, 3 subjects reported procedural headache, 5 subjects reported procedural pain, and 2 subjects reported vomiting. There were no TEAEs reported for clinical laboratories, safety electrocardiograms, or vital signs.

Concerning cardiovascular safety, a thorough analysis of ECGs demonstrated that NYX-2925 did not increase QTc at any dose up to 1200 mg. The maximum geometric mean peak plasma concentration (C_{max}) (20.1 µg/ml) was well above the expected exposure in clinical care. There were no clinically significant changes in HR, PR and QRS or in ECG diagnostic statements.

The pharmacokinetics of NYX-2925 in humans are similar to the pharmacokinetics in rats and dogs. Pharmacokinetic analysis revealed that absorption of NYX-2925 was relatively rapid and peak concentrations were achieved within 2 hours after dosing and declined in a roughly monophasic manner over 24 hours. The pharmacokinetics were dose proportional over the dose range tested (within the variability) and showed minimal accumulation following once per day dosing for 7 days. A high-fat, high-caloric meal decreased the rate of absorption (delayed T_{max}), lowered C_{max} by 10%, but had no impact on the extent of exposure (area under the plasma concentration versus time curve [AUC] values were comparable), suggesting that the compound may be administered with or without food. The majority, approximately 60% to 70%, of the administered dose was eliminated as unchanged NYX-2925 in the urine. The central nervous system exposure was confirmed from the CSF concentration time profile in both CSF dose groups. The CSF concentrations increased proportionally as the dose increased.

In summary, NYX-2925 has been sufficiently tested in preclinical studies for safety and tolerability over a wide dose range, with exposures greater than the proposed clinical doses. General toxicology studies support clinical studies up to and including 6 weeks of daily doses. Results from the first-in-human study indicate that NYX-2925 is safe and well-tolerated in the male and female healthy volunteers dosed to date at single doses up to 1200 mg, and multiple doses up to 900 mg given daily for 7 days. The preclinical and phase 1 clinical data support further testing in humans.

In addition to the current trial, there are 2 other ongoing clinical studies with NYX-2925. NYX-2925-1003 is a phase 1, double-blind, placebo-controlled, pilot, crossover study to assess the effects of NYX-2925 on sleep architecture as assessed by polysomnography in healthy male subjects aged 40-55 when their bedtime is advanced by 3 hours in a sleep laboratory. Also ongoing is study NYX-2925-2002, in subjects with fibromyalgia. The primary objective of this study is to determine whether NYX-2925 modulates central nervous system activity in key pain neural circuitry, consistent with the potential to provide analgesia in subjects with fibromyalgia, as assessed by neuroimaging methods. Secondarily, this study will provide a preliminary characterization of the safety of NYX-2925 in subjects with fibromyalgia.

Further, there is planned study; a phase 1, double-blind, randomized, sponsor-open, parallel, placebo-controlled exploratory study to assess the effect of multiple dose levels of NYX-2925 on

the brain function of healthy volunteers as measured by electroencephalogram and event related potentials.

To date, one serious adverse event, cholelithiasis requiring inpatient hospitalization, has been reported in the clinical development program for NYX-2925, that being in the current study, NYX-2925-2001. The event is considered not related to NYX-2925.

This study (NYX-2925-2001) is a randomized, double-blind, placebo-controlled, multiple-dose study to assess the efficacy and safety of NYX-2925 in subjects with neuropathic pain associated with diabetic peripheral neuropathy. NYX-2925 will be provided as capsules for oral administration.

5 STUDY OBJECTIVES AND ENDPOINTS

5.1 Primary Objective

The primary objective of this study is to evaluate the efficacy of multiple dose levels of NYX-2925 versus placebo in treating the neuropathic pain associated with diabetic peripheral neuropathy.

5.2 Secondary Objectives

Secondary objectives of the study are to assess the:

- Effects of multiple dose levels of NYX-2925 versus placebo on pain characteristics, sleep interference, health status, psychological state, and global improvement.
- Safety and tolerability of multiple dose levels of NYX-2925.

5.3 Study Endpoints

5.3.1 Efficacy Endpoints

The primary endpoint is the change in the numerical rating scale (NRS) score assessing average pain intensity in the past 24 hours from baseline (average of Days -7 to -1) to Week 4 (average of Days 22 through 28).

Secondary efficacy endpoints include:

- Change in the mean NRS score for daily worst pain intensity from baseline (average of Days -7 to -1) to Week 4 (average of Days 22 through 28)
- Change in the mean NRS score assessing average pain intensity in the past 24 hours from baseline (average of Days -7 to -1) to each week of treatment (average of Days 1 through 7, Days 8 through 14, and Days 15 through 21)
- Change in the mean NRS score assessing average pain upon walking intensity in the past 24 hours from baseline (average of Days -7 to -1) to each week of treatment (average of Days 1 through 7, Days 8 through 14, Days 15 through 21, and Days 22 through 28)
- Patient Global Impression of Change (PGI-C) at Weeks 2 and 4
- Change in published subscale scores of the Short-Form McGill Pain Questionnaire version 2 (SF-MPQ-2) from baseline (Visit 2) to Week 4
- Change in published subscale scores of the Norfolk Quality of Life Questionnaire Diabetic Neuropathy (QOL-DN) from baseline (Visit 2) to Week 4
- Change in the Insomnia Severity Index from baseline (Visit 2) to Week 2 and Week 4
- Change in published subscale scores of the Hospital Anxiety and Depression Scale (HADS) from baseline (Visit 2) to Week 4

- Change in the mean Daily Sleep Interference Scale (DSIS) score from baseline (average of Days -7 to -1) to each week of treatment (average of Days 1 through 7, Days 8 through 14, Days 15 through 21, and Days 22 through 28)
- Change in the Brief Pain Inventory for Diabetic Peripheral Neuropathy (BPI-DPN) from baseline (Visit 2) to Week 4

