9.2 Efficacy Assessments

9.2.1 Numeric Rating Scale of Pain Intensity (NRS)

The NRS of pain intensity is a unidimensional, segmented numeric version of the visual analog scale. A subject selects a whole number (0 to 10) that best indicates the intensity of his/her pain.

The format consists of a horizontal line which is anchored by terms defining pain levels where 0 represents no pain and 10 represents worst pain imaginable.

Subjects will report at bedtime their average pain intensity, worst pain intensity, and pain upon walking during the past 24 hours, using the 11-point NRS.

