5.1.1 Day 1/Date of First Dose

Day 1 is also referred to in the protocol and CRF as Visit 2, Baseline Visit, and Week 0.

The date of first dosing of study drug is not collected on the CRF because subjects are given study drug to administer themselves. Therefore, it will be assumed that Day 1 is the same day as the first dosing day of study drug for subjects in the safety population later described in the SAP in Section 6.1.

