5.1.4 Baseline and Post-Baseline Values

Unless otherwise specified, the baseline value is defined as the last measurement/assessment collected/derived on Day 1 or screening. Unless otherwise specified, post-baseline values are defined as collected/derived measurements/assessments after Day 1.

For specific questionnaire assessments, missing responses on Day 1 will not be substituted for screening values for the baseline specific questionnaires. If the total score cannot be calculated at Day 1, then the screening visit will be used if the total score can be calculated at screening. If the total score cannot be calculated for both screening and Day 1 visits, then the latest individual values and subscale scores will be used for the baseline. All questions within a specific questionnaire will be paired together in an analysis visit for the baseline records.

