9.1 Primary Efficacy Data

The primary efficacy data for this study is the NRS score assessing average pain intensity in the past 24 hours. Daily collected pain scores are based on an 11-point numerical rating scale/Likert scale ranging from 0 to 10. Where 0 represents no pain and 10 is the worst pain imaginable^[2].

The mean NRS score assessing average pain intensity in the past 24 hours will be calculated for the analysis visits described in Section 5.4.2^[4]:

- Baseline (average of Study Days -7 to -1)
- Week 1 (average of Study Days 1 to 7)
- Week 2 (average of Study Days 8 to 14)
- Week 3 (average of Study Days 15 to 21)
- Week 4 (average of Study Days 22 to 28)

The mean baseline visit will be calculated if at least 6 of the study days have a reported pain score. This is a requirement in order to be eligible for being randomized to a study drug treatment arm. There will need to at least 4 daily pain scores collected within a post-baseline analysis visit in order to calculate the mean pain score for that visit.

Each mean analysis visit score will take on values ranging from 0 to 10 and will be rounded off by one number after the decimal point. Data prior to Study Day -7 or after Study Day 28 will not be used in the mean calculated scores. No missing data imputations will be used for these observed means, but Section 9.1.3 will explain imputation methods used for sensitivity analyses.

The actual means, change from baseline, and percent change from baseline at each analysis visit will be summarized using descriptive statistics. The same descriptive statistics table will be additionally provided by each study site, age groups, gender, race, ethnicity, and subjects using or not using at least 1 concomitant analgesic medication at Baseline. All data collected and derived will be presented in subject listings.

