9.2.9 Daily Sleep Interference Scale (DSIS)

The collection method of the Daily Sleep Interference Scale (DSIS) score has data that is similar to the primary efficacy data described in Section 9.1 for the NRS score assessing average pain intensity in the past 24 hours. However, the study days are shifted by one day based on the analysis visits described in Section 5.4.3 due to the scores are based on sleep from the previous study day:

- Baseline (average of Study Days -6 to 1)
- Week 1 (average of Study Days 2 to 8)
- Week 2 (average of Study Days 9 to 15)
- Week 3 (average of Study Days 16 to 22)
- Week 4 (average of Study Days 23 to 29)

Daily collected scores and are based on an 11-point numerical rating scale/Likert scale ranging from 0 to 10. Where 0 represents "did not interfere with sleep" and 10 is "completely interfered with sleep/unable to sleep" due to pain^[23].

The secondary endpoints of interest with this data is the change in the mean score from baseline to each analysis week of treatment (Weeks 1, 2, 3, and 4). The same analyses methods will be applied to the Daily Sleep Interference Scale (DSIS) score as described in Sections 9.1, 9.1.1 and 9.1.2. No imputation methods for missing data will be applied for these secondary endpoints.

The actual means and change from baseline at each analysis visit will be summarized using descriptive statistics. ANCOVA analyses using the mean change from baseline will be provided for individual models for Weeks 1, 2, 3, and 4 as described in Section 5.3.5.2. A MMRM model will be analyzed for all post-baseline analysis visits (Weeks 1, 2, 3, and 4) for the mean change from baseline as described in Section 5.3.5.3.

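### The Week 1 pain means include the Day 1 bedtime score, whose 24-hour recall reaches back before drug is dispensed, so an early treatment effect is modestly understated.

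*Protocol*

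**What the plan says.** **Window.** Protocol 5.3.1 defines the weekly change in average pain over "each week of treatment (average of Days 1 through 7, Days 8 through 14, and Days 15 through 21", and starts the walking-pain weeks on Day 1 too. SAP 9.1 gives "Week 1 (average of Study Days 1 to 7", matching the table in SAP 5.4.2. SAP 9.2.1 and 9.2.3 carry the same weeks to worst and walking pain. Worst pain at Week 1 is in the SAP only; protocol 5.3.1 lists worst pain at Week 4 alone.

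**Diary.** Protocol 9.2.1: "Subjects will report at bedtime their average pain intensity, worst pain intensity, and pain upon walking during the past 24 hours".

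**Day 1.** SAP 5.1.1: "Day 1 is also referred to in the protocol and CRF as Visit 2, Baseline Visit, and Week 0". Protocol 6.1 and 8.1 place the first dispensing of study drug at that visit.

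**First dose.** SAP 5.1.1: "The date of first dosing of study drug is not collected on the CRF because subjects are given study drug to administer themselves". For the safety population, therefore, "it will be assumed that Day 1 is the same day as the first dosing day of study drug". SAP 8.4 adds that the time was not collected either.

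**Minimum data.** SAP 9.1 requires at least four daily scores for a post-baseline weekly mean.

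**The concern.** The Day 1 entry looks back to bedtime on Day -1. The night and every hour up to dispensing at Visit 2 are untreated, yet the score is averaged as on-treatment data. If the drug has an effect in the first week, a partly untreated day pulls the treatment difference toward zero.

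At stake are nine Week 1 contrasts (three pain measures by three doses), each with an ANCOVA, and the Week 1 column of each pain MMRM. These inform how quickly and at what dose the drug works. The primary endpoint averages Days 22 to 28, so Day 1 plays no part in it.

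**Working it through.** **1. The plan's own figure.** SAP 4.4 gives 75 per group, a difference of 1.05, an SD of 2.25 and two-sided alpha 0.05. The noncentrality is 1.05 / (2.25 × √(2/75)) = 2.86, and the noncentral t gives 81.0% power. At the protocol's alpha of 0.048 it is 80.6%. The stated figure of about 80% reproduces.

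**2. Untreated share of the Day 1 recall.** Bedtime is assumed to be 22:00; the documents give no clock times. With the first dose at hour t on Day 1, the share is s = (24 − (22 − t)) / 24.

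**3. Dilution of the Week 1 difference.** Assume the Day 1 effect is proportional to post-dose hours and the effect is constant from Day 2. A mean of k daily scores including Day 1 then loses the fraction s / k relative to the Day 2 to 7 effect. With k = 7:

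| First dose on Day 1 | s | s / 7 |
|---|---|---|
| 08:00 | 10/24 = 42% | 6.0% |
| 10:00 | 12/24 = 50% | 7.1% |
| 12:00 | 14/24 = 58% | 8.3% |
| 14:00 | 16/24 = 67% | 9.5% |
| 18:00 | 20/24 = 83% | 11.9% |
| 22:00 | 24/24 = 100% | 14.3% |

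**4. Incomplete diaries.** If Day 1 carries no effect (s = 1), a mean that includes it loses 1/6 = 16.7% with six scores, 1/5 = 20% with five and 1/4 = 25% with four, the SAP minimum. These are limits for an individual mean, not for the group difference.

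**5. Power, as illustration only.** Putting the sample-size inputs through the dilution gives:

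- noon dose: 1.05 × (1 − 0.0833) = 0.9625, power 74.0%;
- no Day 1 effect: 1.05 × 6/7 = 0.90, power 68.2%.

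The 1.05 and 2.25 come from published data on other drugs and are not Week 1 values. The documents give no Week 1 effect or SD.

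**6. Precision lost by dropping Day 1.** With equal correlation ρ between daily scores, the variance of a k-day mean is proportional to ρ + (1 − ρ)/k. Going from seven scores to six:

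- ρ = 0.3: √(0.4167 / 0.4000) = 1.021, so the SD rises 2.1%;
- ρ = 0.9: √(0.9167 / 0.9143) = 1.001, so it rises 0.1%.

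Both are below the 6% to 14% loss of signal in step 3. The values of ρ are assumptions.

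**The case against.** The case for leaving the window alone is reasonable. A calendar-week mean is prespecified in both documents and applies equally to every arm, so it creates no false-positive bias. Week 1 is a secondary time point in a phase 2 study without multiplicity control. Protocol section 4 reports peak concentrations within 2 hours of dosing, so the Day 1 score may carry some effect. All of this stands and keeps the point small. It does not explain why a score that always includes untreated hours should count as treatment.

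Several stronger readings are tempting, but the documents do not support them:

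- **That the Day 1 recall is mostly pre-dose.** With a 22:00 bedtime this needs a dose after 10:00. That is plausible, but no dose time is recorded.
- **That the SAP corrects this problem for sleep.** SAP 9.2.9 says "However, the study days are shifted by one day based on the analysis visits described in" section 5.4.3, but its reason is that a morning entry describes the previous study day. Entries on Days 2 to 8 describe study Days 1 to 7, the same days as the pain window.
- **That pain and sleep have inconsistent baselines.** Sleep entries on Days -6 to 1 (there is no Day 0) describe study Days -7 to -1, which is the pain baseline.
- **That SAP 5.1.4 is contradicted.** It says "post-baseline values are defined as collected/derived measurements/assessments after Day 1", but the sentence opens by allowing exceptions, and SAP 5.4.2 and 9.1 specify one for pain.
- **That Week 1 is the only read on onset.** SAP 9.3.3 and 9.3.4 plan time to response and time to sustained reduction.
- **That Week 1 power falls from 81% to about 68%.** That borrows inputs not meant for Week 1 and assumes the full effect from Day 2 and none on Day 1.

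**Conclusion.** The point holds as a small, avoidable bias toward no difference in the Week 1 pain comparisons. Its size is about 6% to 14% for a complete diary and up to 25% for an individual mean resting on four scores.

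The 6% to 14% range depends on a 22:00 bedtime, a first dose between 08:00 and bedtime on Day 1, an effect proportional to post-dose hours that day, and a constant effect afterwards. The true share cannot be recovered from the data collected. With a slower onset, a fully treated first day would have shown little effect anyway, so less of the shortfall comes from untreated hours. With no effect in Week 1 there is nothing to dilute.

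Weeks 2 to 4 and the primary ANCOVA are unaffected.

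**What to change.** Define the Week 1 window for the pain scores as Days 2 to 7, still requiring at least four scores, and show the Day 1 score in listings only. Make the change together in:

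- the protocol synopsis, 5.3.1, 12.5.1.2 and 12.5.2 (pain entries only);
- SAP 5.4.2, 9.1, 9.2.1 to 9.2.3 and 9.3.1, including the rescue-adjusted Week 1 mean.

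Changing only some of these would create contradictions where the documents now agree. Leave Weeks 2 to 4 and the primary endpoint as they are. SAP 9.1.3 (daily imputation) and SAP 9.3.3 (time to response) also start at Study Day 1 but do not use the Week 1 window. A sentence should say whether that start day is intended.

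The cost is wording and one window in the derivation program. Week 1 rests on six rather than seven daily scores, and it no longer matches exactly the study days described by the sleep scale's Week 1 window. If the sponsor prefers to keep Days 1 to 7, the minimum is a prespecified Days 2 to 7 sensitivity analysis and a stated reason for keeping Day 1.
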